**Listing 5.10.1-1 Patients with fatal AEs – Safety set (XX AEs reported by XX patients)**

Patient identification number	Inclusion date	Number of cycles received	Adverse Event								
			Number	Description	Onset date	Event period	Date when AE became serious	Highest intensity	GA101		Outcome
XXXXX	XX/XX/XXXX	X	Yes	XXXXX	XX/XX/XXXX	XX	XX/XX/XXXX	X	X	XX	XXX

**Listing 5.10.1-2 Patients with AEs leading to treatment discontinuation – Safety set (XX AEs reported by XX patients)**

Patient identification number	Inclusion date	Number of cycles received	Adverse Event								
			Number	Description	Onset date	Event period	Date when AE became serious	Highest intensity	GA101		Outcome
XXXXX	XX/XX/XXXX	X	Yes	XXXXX	XX/XX/XXXX	XX	XX/XX/XXXX	X	X	XX	XXX

**Listing 5.10.1-3 Patients with AESI\* – Safety set (XX AEs reported by XX patients)**

Patient identification number	Inclusion date	Number of cycles received	Adverse Event								
			Number	Description	Onset date	Event period	Date when AE became serious	Highest intensity	GA101		Outcome
XXXXX	XX/XX/XXXX	X	Yes	XXXXX	XX/XX/XXXX	XX	XX/XX/XXXX	X	X	XX	XXX

\* AESI = Tumor Lysis Syndrom and IRR grade 4 occurring during or within 24 hours after the GA101 infusion

## 5.10.2 Serious Adverse Events

**Table 5.102-2 Summary of SAEs – Safety set**

		Safety set N=XX
Patients with at least one SAE		
No		XX (XX.X%)
Yes		XX (XX.X%)
Patient with at least one related SAE		
No		XX (XX.X%)
Yes		XX (XX.X%)
Patient with at least one SAE of grade >= 3		
No		XX (XX.X%)
Yes		XX (XX.X%)

**Table 5.102-3 SAEs by SOC and PT – Safety set**

	Safety set N=XX
AEs	XX (XX.X%)
SOC 1	XX (XX.X%)
PT 1	XX (XX.X%)
PT ...	XX (XX.X%)
SOC ...	XX (XX.X%)
PT 1	XX (XX.X%)
PT ...	XX (XX.X%)

**Table 5.102-3 Related SAEs by SOC and PT – Safety set**

	Safety set N=XX
Related SAEs	XX (XX.X%)
SOC 1	XX (XX.X%)
PT 1	XX (XX.X%)
PT ...	XX (XX.X%)
SOC ...	XX (XX.X%)
PT 1	XX (XX.X%)
PT ...	XX (XX.X%)

**Table 5.102-4 Characteristics of SAEs – Safety set**

		Safety set N=XX
Onset period		
Pre-phase		XX (XX.X%)
Induction		XX (XX.X%)
ASCT		XX (XX.X%)
Maintenance		XX (XX.X%)
Maintenance on-demand		XX (XX.X%)
Follow-up		XX (XX.X%)
Highest intensity		
1		XX (XX.X%)
2		XX (XX.X%)
3		XX (XX.X%)
4		XX (XX.X%)
5		XX (XX.X%)
Relationship with GA101		
Unrelated		XX (XX.X%)
Related		XX (XX.X%)
Not applicable		XX (XX.X%)
Relationship with DHAP		
Unrelated		XX (XX.X%)
Related		XX (XX.X%)
Not applicable		XX (XX.X%)
Relationship with ASCT		
Unrelated		XX (XX.X%)
Related		XX (XX.X%)
Not applicable		XX (XX.X%)
Serious AE		
No		XX (XX.X%)
Yes		XX (XX.X%)
AESI*		
No		XX (XX.X%)
Yes		XX (XX.X%)
Outcome		
Not recovered/Not resolved		XX (XX.X%)
Recovered/Resolved		XX (XX.X%)
Recovered/Resolved with sequelae		XX (XX.X%)
Recovering/Resolving		XX (XX.X%)
Fatal		XX (XX.X%)

\* AESI = Tumor Lysis Syndrom and IRR grade 4 occurring during or within 24 hours after the GA101 infusion

**Listing 5.10.2-2 Patients with SAEs – Safety set (XX SAEs reported by XX patients)**

Patient identification number	Inclusion date	Number of cycles received	Adverse Event							
			Number	Description	Onset date	Event period	Date when AE became serious	Highest intensity	GA101	Outcome
XXXXX	XX/XX/XXXX	X	Yes	XXXXX	XX/XX/XXXX	XX	XX/XX/XXXX	X	X	XX

### 5.10.3 Other Primary Malignancy (OPM)

**Table 5.10.4 OPM – Safety set**

		Safety set N=XX
Patients with at least one OPM		
No		XX (XX.X%)
Yes		XX (XX.X%)
If yes, number of OPMs by patient		
N		XX
Missing		XX
Mean (SD)		XX.X (XX.XX)
Median		XX.X
Q1 ; Q3		XX ; XX
Min ; Max		XX ; XX
If yes, time to onset of 1st OPM since inclusion (months)		
N		XX
Missing		XX
Mean (SD)		XX.X (XX.XX)
Median		XX.X
Q1 ; Q3		XX ; XX
Min ; Max		XX ; XX

**Table 5.10-5 OPM by SOC and PT – Safety set**

	Safety set N=XX	
	Patients	Events
OPM	XX (XX.X%)	XX
SOC 1	XX (XX.X%)	XX
PT 1	XX (XX.X%)	XX
PT ...	XX (XX.X%)	XX
SOC ...	XX (XX.X%)	XX
PT 1	XX (XX.X%)	XX
PT ...	XX (XX.X%)	XX

**Listing 5.10-1 OPM – Safety set (XX patients)**

Patient identification number	Inclusion date	OPM			Death			Study duration (months)
		Date	Time since inclusion (months)	Description	Y/N	Cause	Other concurrent illness description	
XXXXX	XX/XX/XXXX	XX/XX/XXXX	XX	XXX	XX	XXX	XXX	XXX

**Listing 5.10-2 Narratives of OPMs – Safety set (XX patients)**

Patient identification number	Inclusion date	OPM		
		Date	Description	Narrative
XXXXX	XX/XX/XXXX	XX/XX/XXXX	XX	XX

### 5.10.4 Deaths

**Table 5.10-6 Deaths – Safety set**

		Safety set N=XX
Death		
No		XX (XX.X%)
Yes		XX (XX.X%)
If yes, cause of death		
Lymphoma		XX (XX.X%)
Toxicity of study treatment (including related cancer)		XX (XX.X%)
Concurrent illness		XX (XX.X%)
Toxicity of additional treatment		XX (XX.X%)
Other cause		XX (XX.X%)
Unknown		XX (XX.X%)
If yes, phase of death		
Induction phase		XX (XX.X%)
ASCT		XX (XX.X%)
Maintenance phase		XX (XX.X%)
Follow-Up		XX (XX.X%)
Disease status at death		
Complete response		XX (XX.X%)
Unconfirmed Complete response		XX (XX.X%)
Partial response		XX (XX.X%)
Stable disease		XX (XX.X%)
Progressive disease		XX (XX.X%)
Not evaluated		XX (XX.X%)

**Listing 5.10.4-3 Deaths – Safety set (XX patients)**

Patient identification number	Inclusion date	Number of cycles received	Study duration (months)	Death				
				Date	Cause	Specification of concurrent illness	Specification of other concurrent illness	Specification of other reason
XXXXX	XX/XX/XXXX	X	XX.X	XX/XX/XXXX	XXXXX	XXXXX	XXXXX	XXXXX

**Listing 5.10.4-4 Narratives of fatal SAE – Safety set (XX patients)**

Patient identification number	Inclusion date	OPM		
		Date	Description	Narrative
XXXXX	XX/XX/XXXX	XX/XX/XXXX	XX	XX

## 5.10.5 Clinical Laboratory

**Table 5.10-7 Hematology from baseline to End of Treatment – Safety set**

	Baseline N=XX	End of induction N=XX	ASCT N=XX	After 3y of maintenance N=XX	EoT N=XX
Hematology done					
No	XX (XX.X%)	XX (XX.X%)	XX (XX.X%)	XX (XX.X%)	XX (XX.X%)
Yes	XX (XX.X%)	XX (XX.X%)	XX (XX.X%)	XX (XX.X%)	XX (XX.X%)
If yes,					
Hemoglobin (g/dL)					
N	XX	XX	XX	XX	XX
Missing	XX	XX	XX	XX	XX
Mean (SD)	XX.X (XX.XX)	XX.X (XX.XX)	XX.X (XX.XX)	XX.X (XX.XX)	XX.X (XX.XX)
Median	XX.X	XX.X	XX.X	XX.X	XX.X
Q1 ; Q3	XX ; XX	XX ; XX	XX ; XX	XX ; XX	XX ; XX
Min ; Max	XX ; XX	XX ; XX	XX ; XX	XX ; XX	XX ; XX
Min ; Max	XX ; XX	XX ; XX	XX ; XX	XX ; XX	XX ; XX
Leukocytes (g/L)					
N	XX	XX	XX	XX	XX
Missing	XX	XX	XX	XX	XX
Mean (SD)	XX.X (XX.XX)	XX.X (XX.XX)	XX.X (XX.XX)	XX.X (XX.XX)	XX.X (XX.XX)
Median	XX.X	XX.X	XX.X	XX.X	XX.X
Q1 ; Q3	XX ; XX	XX ; XX	XX ; XX	XX ; XX	XX ; XX
Min ; Max	XX ; XX	XX ; XX	XX ; XX	XX ; XX	XX ; XX
Min ; Max	XX ; XX	XX ; XX	XX ; XX	XX ; XX	XX ; XX
Neutrophils (g/L)					
N	XX	XX	XX	XX	XX
Missing	XX	XX	XX	XX	XX
Mean (SD)	XX.X (XX.XX)	XX.X (XX.XX)	XX.X (XX.XX)	XX.X (XX.XX)	XX.X (XX.XX)
Median	XX.X	XX.X	XX.X	XX.X	XX.X
Q1 ; Q3	XX ; XX	XX ; XX	XX ; XX	XX ; XX	XX ; XX
Min ; Max	XX ; XX	XX ; XX	XX ; XX	XX ; XX	XX ; XX
Min ; Max	XX ; XX	XX ; XX	XX ; XX	XX ; XX	XX ; XX
Lymphocytes (g/L)					
N	XX	XX	XX	XX	XX
Missing	XX	XX	XX	XX	XX
Mean (SD)	XX.X (XX.XX)	XX.X (XX.XX)	XX.X (XX.XX)	XX.X (XX.XX)	XX.X (XX.XX)
Median	XX.X	XX.X	XX.X	XX.X	XX.X
Q1 ; Q3	XX ; XX	XX ; XX	XX ; XX	XX ; XX	XX ; XX
Min ; Max	XX ; XX	XX ; XX	XX ; XX	XX ; XX	XX ; XX
Min ; Max	XX ; XX	XX ; XX	XX ; XX	XX ; XX	XX ; XX
Presence of lymphoma cells (g/L)					
N	XX	XX	XX	XX	XX
Missing	XX	XX	XX	XX	XX
Mean (SD)	XX.X (XX.XX)	XX.X (XX.XX)	XX.X (XX.XX)	XX.X (XX.XX)	XX.X (XX.XX)
Median	XX.X	XX.X	XX.X	XX.X	XX.X
Q1 ; Q3	XX ; XX	XX ; XX	XX ; XX	XX ; XX	XX ; XX
Min ; Max	XX ; XX	XX ; XX	XX ; XX	XX ; XX	XX ; XX
Min ; Max	XX ; XX	XX ; XX	XX ; XX	XX ; XX	XX ; XX
Platelets (g/L)					
N	XX	XX	XX	XX	XX
Missing	XX	XX	XX	XX	XX
Mean (SD)	XX.X (XX.XX)	XX.X (XX.XX)	XX.X (XX.XX)	XX.X (XX.XX)	XX.X (XX.XX)
Median	XX.X	XX.X	XX.X	XX.X	XX.X
Q1 ; Q3	XX ; XX	XX ; XX	XX ; XX	XX ; XX	XX ; XX
Min ; Max	XX ; XX	XX ; XX	XX ; XX	XX ; XX	XX ; XX
Min ; Max	XX ; XX	XX ; XX	XX ; XX	XX ; XX	XX ; XX

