7 STUDY DESIGN

This study is a multicentric, single arm phase II trial to evaluate the efficacy of upfront obinutuzumab in mantle cell lymphoma patients treated by DHAP followed by autologous transplantation plus obinutuzumab maintenance then MRD driven maintenance.

Patients will be recruited over about 2 years and followed until 6.5 years after the last patient included.

The theoretical study dates (start / end) are:

- 1st patient included (FPFV): Q4 2016
- Last patient included (LPFV): Q3 2018
- Last patient followed for principal analysis: Q1 2025

It is expected about 83 patients to have 70 evaluable patients included in the study.

The duration of the treatment period is approximately:

- induction: 12 weeks for 4 cycles of chemotherapy
- conditioning regimen: 8 days
- maintenance : 3 years
- maintenance “on-demand” : 3 years

End of study is defined as the last visit of the last patient in follow-up planned by the protocol.

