9.4 Baseline examination

The subject's eligibility has to be evaluated during the baseline period prior to the first administration of the study drug. The assessments are to be conducted **within 28 days** (or within 14 days for biology tests) before administration of the study treatment:

- Age, gender, weight, height, BSA
- Surgical biopsy (avoid needle biopsies if possible to secure enough material) of tumour tissue for morphology and immunochemistry. A tumor biopsy must be made available during the trial for confirmation of the disease (see section 11.2)
- CT scan with IV contrast of neck, thorax and abdomen/pelvis
- Baseline PET scan (PET0)
- Bone marrow biopsy and bone marrow aspiration for local diagnosis
- Gastroscopy/colonoscopy and other examinations if clinically indicated
- Exploratory lumbar puncture if clinically indicated
- Staging (see Appendix 4 "Ann Arbor staging")
- Clinical examination (including tumor assessment)
- ECOG Performance Status (see Appendix 6 "Performance Status Criteria")
- Relevant medical history
 - Any abnormal medical condition, already present before ICF signature, not due to lymphoma will be reported on medical history pages and for laboratory abnormal value: on haematology/biochemistry pages.
- Blood cell count : Hemoglobin, leukocyte count, neutrophils, lymphocytes, platelets and lymphoma cells
- Biochemical tests: serum creatinin, calculated creatinine clearance according to Cockroft-Gault, total bilirubin, ALAT, ASAT, albumin, LDH
- HIV, HBV (Ag HBs, Ac anti-HBs and Ac anti-HBc) and HCV serologies
- Pregnancy test
- ECG

- **Samples for MRD study**, (cf. Paragraph 11.3 MRD analysis and Appendix 13 “Biological studies”) after informed consent: blood sampling and bone marrow aspiration.

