9.5 Evaluation during induction

	When
Weight and body surface area (see Appendix 5 “Body surface area”)	D-1 or D1 of each cycle
Clinical examination	D-1 or D1 of each cycle
ECOG PS	D-1 or D1 of each cycle
Biochemical tests: serum creatinin, creatinin clearance according to Cockroft-Gault formula, ASAT, ALAT, total bilirubin and LDH	D-1 or D1 of each cycle
Blood cell counts: Hemoglobin, leukocyte count, neutrophils, lymphocytes, platelets and lymphoma cells	D-1 or D1 of each cycle + D7 or D8 and D14 or D15 at cycle 1
The adverse events reporting	Continuous

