9.6 Evaluation after induction and before Autologous Stem Cell Transplant

The pre-transplant assessment and the autologous transplantation have to be performed according to local practices.

	When
Weight and body surface area (see Appendix 5 “Body surface area”)	1 day before GA101-BEAM or at D1
Clinical examination	1 day before GA101-BEAM or at D1
ECOG PS	1 day before GA101-BEAM or at D1
Biochemical tests: serum creatinin, creatinin clearance according to Cockroft-Gault formula, ASAT, ALAT, total bilirubin	1 day before GA101-BEAM or at D1
Complete blood cell counts : Hemoglobin, leukocyte count, neutrophils, lymphocytes, platelets and lymphoma cells	1 day before GA101-BEAM or at D1
Bone marrow aspirate and biopsy if previously positive according to local diagnosis	Between 4 weeks after D1 of cycle 4 and before GA101-BEAM
Thorax, abdomen and pelvis CT with IV contrast (Disease response assessment results must be available and reviewed by the investigator before the first dose of study drug in the next planned cycle)	Between 4 weeks after D1 of cycle 4 and before GA101-BEAM
FDG-PET	Between 4 weeks after D1 of cycle 4 and before GA101-BEAM
Evaluation of the disease response (Cheson 1999 / the Lugano classification 2014)	Between 4 weeks after D1 of cycle 4 and before GA101-BEAM
Any other evaluations or procedures performed at baseline for evaluation of the disease response	Between 4 weeks after D1 of cycle 4 and before GA101-BEAM
Samples for MRD study: blood sampling and bone marrow (BM) aspiration	Between 4 weeks after D1 of cycle 4 and before GA101-BEAM
The adverse events reporting	Continuous

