14.2 Adverse Events reporting rules

Due to expected toxicity of study treatment, all AEs of grade 3-5 for toxicities (hematological or non-hematological) (CTCAE – version 4.0) regardless relationship to investigational product occurring from the date of informed consent signature to 28 days after the last study drug administration of the study will be recorded in the AE pages of the eCRF. When associated to a SAE and regardless the time of occurrence and the grade, the AE must be reported as "Adverse Event" in the appropriate eCRF pages.

Whenever possible, symptoms should be grouped as a single syndrome or diagnosis. The investigator should specify the date of onset, intensity, action taken regarding trial medication, corrective therapy given, outcome of all AEs and his opinion as to whether the AE can be related to the study drugs.

All events that meet one or more criteria of seriousness (see Section 13.1.2.) will be reported as SAE (see Section 13.3).

General AE reporting rules:

- Non-serious AE will be reported through eCRF
- Any episode of any grade of toxicity, related to a SAE must be reported as "Adverse Event" in the appropriate eCRF pages regardless the time of occurrence
- Signs, symptoms and physical findings indicative of lymphoma or progression of lymphoma are not to be reported as "Adverse Event"
- "Alopecia" toxicity (any grade) will never be reported as "Adverse event"
- AEs will be considered ended (recovered without sequelae) when recovered to a grade 0 or baseline
- In case of screening failure, at least AEs corresponding to SAEs will be reported in the AEs pages of eCRF.
- When a medical history resolves or decreases at a grade lower than baseline, the new grade will be the new reference grade for following AEs
- For laboratory abnormalities, the laboratory test to be taken as reference will be the one performed nearest to the Cycle 1 Day 1.

Abnormal laboratory values reporting rules:

If a laboratory abnormality is one component of a diagnosis or syndrome (e.g., alkaline phosphatase and bilirubin 5 × ULN associated with cholecystitis), only the diagnosis (e.g., cholecystitis) or syndrome should be recorded on the AE page/screen of the eCRF. If the laboratory abnormality was not a part of diagnosis or syndrome, the laboratory abnormality should be recorded as an AE.

An abnormal laboratory value which is not a component of a diagnosis or syndrome is considered as an AE if the abnormality:

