- results in discontinuation from the study; or
- requires treatment, modification/ interruption of IP dose, or any other therapeutic intervention; or
- is judged to be of significant clinical importance.

The investigator has to notify in the patient medical file all abnormal laboratory values considered as clinically significant (write next to each abnormal laboratory value assessed as clinically significant "CS" or precise it in the medical report).

Regardless of severity grade, only laboratory abnormalities that fulfill the seriousness criterion need to be documented as a serious adverse event.

During the transplant period (that is to say the period from the first day of hospitalization to the day before C1 Obinutuzumab maintenance), neutropenia and thrombocytopenia resulting from bone marrow aplasia will not be recorded as AEs in the eCRF. Only the following have to be recorded in the eCRF:

- any evolution of ongoing AE
- any new AE related, or that appears to be related, to Obinutuzumab
- any new infection from at least grade 3
- any new oral mucositis from at least grade 3
- any AE fulfilling seriousness criteria

A special attention is required for the following AEs:

- ICU admission whatever the cause
- Clinically Significant Neurological disorders
- Creatinin increased > 1.5 baseline

- Documented germ infection
- Prolongation of hospitalization beyond J 25 after stem cell reinfusion whatever the cause
- AE deemed unusual by the investigator

Please note that AEs of at least grade 3 associated with Stem Cell mobilization should be recorded in the eCRF

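### SAP Table 5.10-7 cannot give the incidence of grade 3-4 cytopenia, and the adverse-event figure that can be read may be too low and is not split by period

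*SAP*

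**What the plan says.** **Laboratory output.** SAP Table 5.10-7, "Hematology from baseline to End of Treatment", has five columns: baseline, end of induction, ASCT, after 3 years of maintenance, and end of treatment. For each blood-count parameter it gives N, missing, mean (SD), median, quartiles and range. No table or listing in the SAP assigns a CTCAE grade to a laboratory value, or shows a nadir, worst value or shift from baseline.

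**Counts scheduled.** Protocol 9.4 to 9.9 require a count at baseline, during induction at "D-1 or D1 of each cycle + D7 or D8 and D14 or D15 at cycle 1", before and after transplant, before each maintenance infusion, at on-demand visits, and at end of treatment.

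**What becomes an AE.** Protocol 14.2 opens by requiring that grade 3-5 AEs, hematological ones included, be recorded. On isolated laboratory abnormalities it then says: "If the laboratory abnormality was not a part of diagnosis or syndrome, the laboratory abnormality should be recorded as an AE". The next sentence reads "An abnormal laboratory value which is not a component of a diagnosis or syndrome is considered as an AE if the abnormality" and lists three conditions: it results in discontinuation; it requires treatment, a dose modification or interruption, or another intervention; or it "is judged to be of significant clinical importance". Neutropenia and thrombocytopenia from marrow aplasia in the transplant period are not recorded as AEs.

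**AE outputs.** SAP Table 5.101-4 gives patients and events by preferred term in grade 3, 4 and 5 columns, over the whole study. SAP 3.2.3 says that AEs will be described by system organ class and preferred term by period. The by-period summaries (Tables 5.101-1 and 5.101-2) have columns for induction, ASCT, maintenance and total, and no preferred-term rows.

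**The concern.** Protocol 10.3.1.2 names neutropenia and thrombocytopenia, the latter including life-threatening cases, as hematological risks of obinutuzumab. Tolerability at induction and then on-demand is a secondary objective (Protocol 6.2, SAP 3.1.2). A reader of the final report will want to know how many patients had a grade 3 or 4 cytopenia, and in which phase.

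There are two possible sources. The laboratory table cannot answer, because a mean or range at a visit does not say how many patients crossed a grade boundary at any time. The AE tables can answer only as well as the events were recorded, and the recording rule reads two ways. Take a grade 3-4 neutropenia that needs no treatment, prompts no dose action and is not judged important. The first sentence makes it an AE and the second does not. If sites read the rule differently, the reported incidence mixes two definitions, and no laboratory-based output in the SAP would reveal it.

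**Working it through.** **Step 1: reproduce the plan's own figure.** Protocol 10.2.3 gives one infusion every 2 months for 3 years: 36/2 = 18, or 36/2 + 1 = 19 if both ends count. SAP Table 4.7-3 lists maintenance visits V1 to V19, so 19 is reproduced. The documents state no total number of blood counts; the rest is a count from the schedule.

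**Step 2: scheduled counts for a full course, informative MRD, MRD-negative on-demand.**

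| Period | Source | Counts |
|---|---|---|
| Baseline | Protocol 9.4 | 1 |
| Induction, 4 cycles ("induction: 12 weeks for 4 cycles of chemotherapy") | Protocol 9.5 | 4 + 2 = 6 |
| Before ASCT, "1 day before GA101-BEAM or at D1" | Protocol 9.6 | 1 |
| After aplasia, before maintenance | Protocol 9.7 | 1 |
| Maintenance | Protocol 9.8, 10.2.3 | 18 or 19 |
| On-demand, every 3 months | Protocol 9.8 | 36/3 = 12 |
| End of treatment | Protocol 9.9 | 1 |

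Total: 1 + 6 + 1 + 1 + 18 + 12 + 1 = 40, or 41 with 19 maintenance visits. If the baseline count is also the cycle 1 day 1 count, and the post-transplant count is also the first maintenance count, the total is 40 - 2 = 38.

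**Step 3: other patients.**
- MRD-positive throughout on-demand: 36 monthly counts, or 38 with days 8 and 15 of the first month. Total 28 + 36 = 64 to 29 + 38 = 67.
- No on-demand phase: 40 - 12 = 28, or 29. A non-informative patient with 3 years of follow-up visits adds 8 + 2 = 10, giving about 38.
- Treatment stopped after induction: 1 + 6 + 1 = 8.

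**Step 4: share used by the table.** For the MRD-negative full course, 5/41 = 12.2% to 5/38 = 13.2%. For MRD-positive throughout, 5/67 = 7.5% to 5/64 = 7.8%. Within 3-year maintenance, 1/19 = 5.3% to 1/18 = 5.6%.

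**Step 5: where the five points fall.** I take the end-of-induction column as the count before GA-BEAM, which starts 4 to 8 weeks after day 1 of cycle 4 (Protocol 10.2.2), and the ASCT column as the count after aplasia. With baseline, these are pre-treatment or recovery points. No column lies inside an induction cycle. The on-demand phase has no column of its own; only end of treatment touches it.

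**Step 6: which AE table could fill the gap.**

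| SAP table | Grade | Preferred term | Period |
|---|---|---|---|
| 5.101-1, 5.101-2 | grade 3 or more, yes/no | no | induction, ASCT, maintenance, total |
| 5.101-3 | no | yes | pooled |
| 5.101-4 | 3, 4, 5 | yes | pooled |
| 5.101-5 | 1 to 5 | no | onset period, including on-demand |

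No table crosses grade and preferred term with period. Overall reported grade 3-4 neutropenia can be read; grade 3-4 neutropenia during on-demand cannot.

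**The case against.** A reader might infer that grade 3-4 cytopenia incidence cannot be read at all. That goes too far. Protocol 14.2 opens by requiring grade 3-5 hematological AEs to be recorded, and Table 5.101-4 shows them by grade and preferred term. The exclusion of transplant aplasia also suggests that cytopenias are otherwise meant to be recorded, and the third condition in 14.2 gives the investigator a route to record any value thought important. These arguments stand against the claim that no figure exists. They do not show that the figure is complete. Under the conditional sentence, recording can turn on judgement alone: Protocol 10.3.1.2.3 lets the day 8 and day 15 infusions of cycle 1 go ahead at any neutrophil count under stated conditions, and gives no neutrophil threshold for maintenance, so a low count need not trigger a dose action. Source verification (Protocol 16.2) checks entries against records, but does not settle which sentence applies.

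A reader might also take 40 counts as a minimum for every patient. It is not; Step 3 gives totals down to 8.

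Nor does the share in Step 4 measure lost incidence. Most unused induction counts are themselves pre-dose, and DHAP is postponed below stated thresholds (Protocol 10.3.1.1). Only two scheduled induction counts fall inside a cycle, both in cycle 1. A worst-grade table from scheduled counts would still miss many nadirs in cycles 2 to 4.

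Finally, it is tempting to say that all the counts are already in the database. The documents schedule them and mention hematology pages, but do not say that every count is entered.

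The SAP promises only that laboratory measurements will be described, and it does that. The point changes no endpoint and no decision rule.

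**Conclusion.** The point holds in this form. Laboratory-based grade 3-4 cytopenia incidence cannot be derived from Table 5.10-7, because it contains no grade, worst value or shift, whatever the number of columns. The table draws on about 5 of 38 to 41 scheduled counts for an MRD-negative full-course patient with informative MRD, and 1 of 18 to 19 in maintenance. The AE-based incidence in Table 5.101-4 can be read, but three limits apply: possible under-ascertainment from the conflict in 14.2, exclusion of transplant aplasia by design, and pooling over periods contrary to SAP 3.2.3. The by-period summaries also lack an on-demand column, although on-demand tolerability is a stated objective.

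The size of any under-ascertainment cannot be calculated from the documents; it depends on how sites read 14.2. The conclusion assumes that the SAP's table shells are the complete planned output. This is an inexpensive improvement to safety reporting and does not threaten the primary result.

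**What to change.** 1. Add to SAP 5.10.5 a table of worst post-baseline CTCAE grade per patient for neutrophils, platelets and hemoglobin, with columns for induction, maintenance and on-demand. Use all counts recorded in the eCRF, unscheduled ones included. Show the number of patients with at least one count and the number of counts per patient in each period. Show the baseline grade beside it, since Protocol 8.2 admits low neutrophil or platelet counts caused by marrow infiltration. State to which period the count before GA-BEAM belongs.
2. Add a footnote that scheduled counts are mostly pre-dose, so the induction column is a lower bound for nadirs.
3. Split Table 5.101-4 by period, with an on-demand column, as SAP 3.2.3 promises, and add that column to Tables 5.101-1 and 5.101-2.
4. Reconcile the two sentences in Protocol 14.2, and state in the SAP which rule the AE data followed, or that it may have varied by site.

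**Cost.** Items 1 to 3 are derived tables and need no new patient procedure, provided the counts were entered; the number-of-counts row will show whether they were. Item 4 costs a sentence in the SAP and, if the protocol text is changed, an amendment with the approvals in Protocol 18.9. With SAP version 2.0 effective in October 2024 and final analysis planned for Q1 2025, editing 14.2 cannot recover AEs that were never recorded. The worst-grade table can show the abnormalities themselves, so far as the counts exist.
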